6.1.3 Inferential Analysis for Adverse Events

95% confidence intervals according to Altman will generally be provided for all AE rates. Differences between the four treatment groups will be assessed for significance using Fisher's exact (Fisher-Freeman-Halton) test, whereby a significant overall test will be amended by pair-wise tests.

It is stated in detail in Section 7 for which tables such comparisons will be made.

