1.2 Study Design

This is a randomized, observer-blind (subject, sponsor and investigator/ site staff involved in clinical evaluation of subjects are blinded), placebo controlled, multicenter Phase 2 study (see Figure 1).

In the Run-in phase, a total of 120 subjects aged 18 to 40 years were to be randomized stratified by study site 1:1:1:1 to receive VLA15 90 µg w/ alum, VLA15 135 µg w/ alum, VLA15 180 µg w/ alum, or placebo (30 subjects per treatment group) as intramuscular (I.M.) vaccinations on Days 1, 29 and 57. Dosing was to be adjusted by injection volume (see Table 1).

Table 1: Treatment Groups and Vaccinations

Group	Treatment	Injection Volume [mL]	Days of Vaccination
90 µg	VLA15 90 µg w/ alum	0.50	1, 29, 57
135 µg	VLA15 135 µg w/ alum	0.75	1, 29, 57
180 µg	VLA15 180 µg w/ alum	1.00	1, 29, 57
Placebo	PBS	1.00	1, 29, 57

Two safety visits were to be performed after the first vaccination: a safety phone call at Day 4 (i.e. Visit 1a, three days after the first vaccination) and an in-person visit at Day 8 (i.e. Visit 1b, seven days after the first vaccination). After all subjects enrolled in the Run-in phase completed Visit 4 (Day 85, i.e. 28 days after the third vaccination) a Data Safety Monitoring Board (DSMB) reviewed all available safety data up to Day 85 in a scheduled DSMB meeting and gave the recommendation that all treatment groups were safe and well tolerated so far and could be continued in the Main Study phase based on available safety data. After the DSMB meeting, the two higher dose groups (135 µg and 180 µg of VLA15 w/ alum) were selected for further investigation. No safety concerns associated with any of the VLA15 treatment groups were identified by the independent DSMB.

In the Main Study phase, a total of 450 subjects aged 18 to 65 years will be randomized stratified by study site, age group and baseline *B.b. s.l.* serostatus 2:2:1 to receive 135 µg or 180 µg VLA15 w/ alum (180 subjects each) or placebo (90 subjects), as I.M. vaccinations on Days 1, 29 and 57. Subjects will be enrolled in two age groups (18-49 years and 50-65 years) in a ratio of approximately 2:1.

In both study phases, target is to enroll approximately 10 % or more of subjects that are baseline seropositive for *Borrelia burgdorferi sensu latu* (*Bb s.l.*). This is aimed to be achieved through selection of endemic recruitment areas as well as database searches for *Bb s.l.* seropositive subjects.

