2.12 Columns in Tables

All tables will be presented by treatment group, i.e. every treatment group will be shown in a separate column. Tables described at overall study information (Section 3), baseline evaluation (Section 4) and safety analysis (Section 6) will show one column per treatment group (i.e. 90 µg, 135 µg, 180 µg and Placebo) a column for the three VLA15 treatment groups pooled and a column for all subjects pooled. Tables defined in Section 5 will show one column for each treatment group. Statistical analyses will pool subjects from both Run-in and Main Study phase.

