5.3 Inferential analysis

- In general, all statistical tests comparing treatment groups in the immunogenicity analysis will only include the two dose groups chosen for the main phase (i.e. VLA15 135 μ g and 180 μ g groups) and the placebo group. However, summary measures for 90 μ g group will be included in the tables.
- ANOVAs with factors treatment group and study sites will be performed for the comparison between the VLA15 135 μ g, 180 μ g and Placebo group for each OspA ST1 to ST6 respectively. The primary immunogenicity analysis will be the ANOVA for ELISA GMTs at Day 85 in the PP Population.
- ANOVAs will be performed for GMTs as well as GMFRs at all available time points.
- This will be done using log10 transformed data and taking the anti-log of the resulting point estimates for the least squares means, least squares means differences and the corresponding 95% CIs. Tukey's HSD test will be applied for pair-wise comparisons.
- Sensitivity analyses for GMTs and GMFRs will be performed for ANOVAs with factors study site, treatment group, study site*treatment group, age, and B.b. s.I serostatus at baseline.
- Summary tables for the OspA- specific IgG titer against each OspA serotype and summary tables for the geometric mean fold-rise against each OspA serotype will be amended by an overall test (Kruskal-Wallis).
- SCRs will be compared using Fisher-Freeman-Halton tests, a significant overall test will be amended by pair-wise tests (Fisher's exact test). The same will be done for rates of subjects reaching a 4- or 10- fold Increase from Day 1 (Visit 1) in titer.
- A non-parametric correlation analysis (Spearman) between OspA IgG antibodies GMTs for each combination of two different OspA specific IgG types will be performed for Day 85 and VLA15 treatment group separately as well as for all VLA15 treatment groups together (pooled analysis).

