7.1.4 Safety

No	Legend	IA D85	IA D236	Content/Comment
Table 14.1.4.1:	Summary Table of Adverse Events (solicited and unsolicited) (Safety Population)	X	X	Including statistical test • Any AE, related AE, severe AE, related

				severe AE, SAE, related SAE, medically attended AE, related medically attended AE, AE leading to withdrawal from study, AE leading to withdrawal from further vaccination 
 • Any solicited AE, severe solicited AE, solicited local AE, severe solicited local AE, solicited systemic AE, severe solicited systemic AE • Any unsolicited AE, related unsolicited AE, severe solicited AE, related severe solicited AE, unsolicited SAE, medically attended unsolicited AE, unsolicited AE leading to withdrawal from study, unsolicited AE leading to withdrawal from further vaccination, AE of special interest, related AE of special interest
Table 14.1.4.2:	Summary Table of Adverse Events by Age group (solicited and unsolicited) (Safety Population)	X	X	Including statistical test Content see table 14.1.4.1
Table 14.1.4.3:	Summary Table of Adverse Events by Region (solicited and unsolicited) (Safety Population)	X	X	Including statistical test Content see table 14.1.4.1
Table 14.1.4.4:	Summary Table of Adverse Events by B.b. s.l. serostatus (solicited and unsolicited) (Safety Population)	X	X	Including statistical test Content see table 14.1.4.1
Table 14.1.4.5:	Summary Table of Adverse Events (solicited and unsolicited) by Vaccination Period (Safety Population)	X	X	Including statistical test Content see table 14.1.4.1
Table 14.1.4.6:	Subjects with Solicited and Unsolicited Serious	X	X	Including statistical test

	Adverse Events by SOC and PT (Safety Population)			
Table 14.1.4.7:	Subjects with Solicited and Unsolicited Related Serious Adverse Events by SOC and PT (Safety Population)	X	X	Including statistical test
Table 14.1.4.8:	Subjects with Solicited and Unsolicited Medically Attended Adverse Events by SOC and PT (Safety Population)	X	X	Including statistical test
Table 14.1.4.9:	Subjects with Solicited and Unsolicited Related Medically Attended Adverse Events by SOC and PT (Safety Population)	X	X	Including statistical test
Table 14.1.4.10:	Subjects with Solicited and Unsolicited Adverse Events Leading to Withdrawal from Further Vaccination by SOC and PT (Safety Population)	X	X	Including statistical test

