7.2 List of Data Listings

7.2.1 Overall Study Information

[figure not shown]
No	Legend	Content
Listing 16.2.1.1.1:	Subject overview	Subject ID, Country, Site Name, Study Part, Date of signed informed consent, Subject eligible to be randomized, Reason not randomized, Planned Treatment, Actual Treatment, Safety/mITT Population, Reason not in Safety/mITT Population, PP Population, Reason not in PP Population
Listing 16.2.1.1.2:	Screening Failure with Reason	Subject ID, Withdrawal of consent, In/Ex criteria not met, Other reason screening failure, Specification of other reason for screening failure
Listing 16.2.1.1.3:	In/Exclusion Criteria that were not Met	Subject ID, Visit, Criterion ID not met, Criterion description
Listing 16.2.1.1.4:	Study Vaccination (Vaccinated Subjects)	Subject ID, Group, Visit, Vaccination administered, Reason if not Administered, Date, Time, Kit number, Location, Other location (specification/reason)
Listing 16.2.1.1.5:	Visit Log (Vaccinated Subjects)	Subject ID, Group, Visit, Visit performed, Visit Date, Reason visit not performed, Deviation from time window [days], Reason outside time window, Age, Reason for unscheduled visit, Type of contact (ET visit)
Listing 16.2.1.1.6:	Missed Visits, Missed Vaccinations, Early Terminations: Part I (Vaccinated Subjects)	Subject ID, Group, Visit attendance, All vaccinations administered, Primary reason treatment discontinuation, Other reason for treatment discontinuation, AE Term (treatment discontinuation), Reason for recommended withdrawal (treatment discontinuation), Individual stopping criteria, AE Term (stopping criteria)
Listing 16.2.1.1.7:	Missed Visits, Missed Vaccinations, Early Terminations: Part II (Vaccinated Subjects)	Subject ID, Group, Is the primary reason for treatment discontinuation the same as for early termination, Primary reason for early termination, Other reason for early termination, AE Term (early termination), Reason for recommended withdrawal (early termination), Death date, Primary cause of death, Date of ET, Last attended scheduled visit before ET

Listing 16.2.1.1.8:	Protocol Deviations (Vaccinated Subjects)	Subject ID, Group, PD Category, PD Description, Severity, Reason for classification

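### The four-group adverse event test pools Run-in and Main data although 90 µg was randomised only in the Run-in, so its p-values mix dose with study phase.

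*SAP*

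**What the plan says.** Section 6.1.3 of the SAP sets the inferential analysis of AE rates: "Differences between the four treatment groups will be assessed for significance using" Fisher's exact (Fisher-Freeman-Halton) test, where "a significant overall test will be amended by pair-wise tests". No stratum or restriction is named. Section 2.12 adds: "Statistical analyses will pool subjects from both Run-in and Main Study phase".

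Section 1.2 describes two separate randomisations. In the Run-in, "a total of 120 subjects aged 18 to 40 years were to be randomized stratified by study site 1:1:1:1" to 90, 135, 180 µg or placebo, 30 per group. The Main phase takes ages 18 to 65 and randomises 450 subjects 2:2:1 to 135 µg, 180 µg and placebo (180, 180 and 90). It has no 90 µg arm. On age in the Main phase: "Subjects will be enrolled in two age groups (18-49 years and 50-65 years) in a ratio of approximately 2:1".

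For immunogenicity, Section 5.3 takes a different line: "all statistical tests comparing treatment groups in the immunogenicity analysis will only include the two dose groups chosen for the main phase" and placebo, with 90 µg summarised only.

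**The concern.** Subjects on 90 µg were randomised alongside only 30 of the 210 planned subjects in each higher dose group and 30 of the 120 on placebo. The other comparators come from a later phase with a wider age range. The SAP also records differences in observation. After vaccination, subjects are watched for at least one hour in the Run-in and at least 30 minutes in the Main phase (note 18 to the Tables of Events). The Day 4 and Day 8 safety contacts are described in Section 1.2 as part of the Run-in account. Either could change AE reporting at the same dose.

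The unstratified four-group test cannot separate these influences from dose. A phase difference alone can make the overall test significant and so open the pair-wise tests. A report that 90 µg has more or fewer AEs than another group could then reflect phase, and could be read as a dose response.

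Section 7.1.4 stratifies some safety tables by age group, region or serostatus, but none by phase. The phase variable does exist, since Listing 16.2.1.1.1 carries it: "Subject ID, Country, Site Name, Study Part, Date of signed informed consent".

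**Working it through.** **Plan figures.** The SAP gives no operating characteristic for the AE test. Its safety sample-size statements in Section 1.4 use the same group sizes and reproduce from 1 − 0.05^(1/n) for zero events:
- n = 30: 9.5% (the SAP says below 10%).
- n = 210: 1.4% (the SAP says 1.4%).

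**Share of each pooled group that comes from the Run-in (Section 1.2).**

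| Group | All ages | Ages 18-49 |
|---|---|---|
| 90 µg | 30/30 = 100% | 30/30 = 100% |
| 135 µg | 30/(30+180) = 14.3% | 30/(30+120) = 20% |
| 180 µg | 30/(30+180) = 14.3% | 30/(30+120) = 20% |
| Placebo | 30/(30+90) = 25% | 30/(30+60) = 33% |

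The 18-49 column applies the planned 2:1 age split to the Main phase, which gives 120, 120 and 60 subjects.

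**Why this biases the test.** With no dose effect, the expected rate in a group is w × (Run-in rate) + (1 − w) × (Main rate), where w is its Run-in share. If the rates are 40% and 30%, this gives 40% for 90 µg, 0.143 × 40 + 0.857 × 30 = 31.4% for 135 and 180 µg, and 0.25 × 40 + 0.75 × 30 = 32.5% for placebo. The groups differ although dose does nothing.

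**Size.** I simulated 10,000 trials per scenario with no dose effect. The overall test was Fisher-Freeman-Halton, and pair-wise Fisher tests counted only after overall p < 0.05. The SAP states no level for the AE tests, so 5% is assumed. The phase rates are also assumed. Cells are the percentage of trials that reject.

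| Run-in / Main rate | 30/30 | 35/30 | 40/30 | 20/30 | 50/30 |
|---|---|---|---|---|---|
| Planned four-group test, all ages | 5.0 | 6.7 | 11.7 | 10.3 | 31.6 |
| Any gated 90 µg contrast | 2.5 | 4.6 | 9.5 | 7.7 | 30.0 |
| Gated 135 vs 180 µg | 1.7 | 1.8 | 2.3 | 2.2 | 2.9 |
| Planned test, ages 18-49 only | 4.5 | 6.5 | 10.1 | 9.0 | 27.2 |
| Three groups pooled, without 90 µg | 4.9 | 4.8 | 5.4 | 5.3 | 6.1 |
| Four groups, Run-in only | 5.2 | 4.9 | 4.6 | 4.5 | 4.9 |

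Repeat runs agree within simulation error: 10.4% to 11.9% at 40/30 and 31.6% to 33.5% at 50/30 for the planned test. At 20% and 10%, a run of 4,000 trials gave 21.0%.

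**Age-group tables.** Tables 14.1.4.2, .17, .21, .26 and .30 remove ages 50-65, but in the 18-49 stratum ages 18-40 (Run-in) are still set against 18-49 (Main). The 18-49 row above assumes that the phase difference persists in that stratum. If it came only from ages 50-65, these tables would remove it.

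**Reach.** Tables 14.1.4.1 to .43 (43) and 14.1.4.48 to .59 (12) are flagged as carrying a statistical test: 43 + 12 = 55 of 74.

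**The case against.** The strongest reply is that nothing is decided on these p-values. Development of 90 µg stopped after the Run-in, the AE tests are secondary, every AE rate gets a 95% CI in any case, and 135 vs 180 µg has the same phase mix in both groups. All of that stands, and it limits the point to the overall AE p-value and the 90 µg contrasts.

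A second reply is that Section 2.14 declares the inclusion of all dose groups as a deliberate change from the protocol. It does, but it says nothing about phase, and Section 5.3 keeps 90 µg out of the immunogenicity tests.

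Third, the size and direction are unknown. With equal phase rates there is no inflation, and a 5-point difference gives 6.7%. For rare events the test can even be conservative: at 0% in the Run-in and 2% in the Main phase it rejects in 1.8%. At 4% and 2%, however, it rejects in 10.4%. This is a fair caution about magnitude and leaves the confounding in place.

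Fourth, in the 50-65 stratum of the age-group tables there are no Run-in subjects, so the problem cannot arise there. That is correct. It remains in the 18-49 stratum of the same tables.

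Finally, the three-group test keeps a small imbalance, because placebo is 25% Run-in against 14.3%. Its rejection rate was at most 6.1% in the scenarios tabulated, and 6.8% over a wider set of assumed rates.

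**Conclusion.** The concern holds. As written, the four-group AE test does not isolate dose. Its overall p-value, which gates the pair-wise tests, and every 90 µg contrast are confounded with study phase. If the Run-in and Main AE rates differ by 10 points around 30%, the false-positive rate of the overall test is about 10% to 12% instead of 5%. It reaches about 32% at an extreme 20-point difference and stays at 5% if there is no difference. These figures rest on assumed phase rates, planned group sizes and a 5% level.

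The primary immunogenicity analysis is not affected, and 135 vs 180 µg is touched only through the gate. Placebo against 135 or 180 µg is barely affected. The change should be made because the affected p-values recur across 55 tables and the correction is cheap.

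**What to change.** Amend Section 6.1.3 along these lines:

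> On pooled data, the overall and pair-wise tests compare 135 µg, 180 µg and placebo only. The 90 µg group is shown descriptively with its rate and 95% CI.

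This brings the AE tests into line with Section 5.3. Section 2.14 should then be adjusted to match.

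If 90 µg is to be tested, do it only within the 120 Run-in subjects (30 per group), with the same overall-then-pair-wise gate. Stratifying the three-group test by phase is optional. If it is used, it should be an exact stratified test, because the tables by system organ class and preferred term are sparse.

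The cost is two sentences and one group dropped from the test call, with no new data. The price is that the tabulated p-values no longer cover 90 µg. Within the Run-in, Fisher's test of 30 vs 30 has about 26% power for 30% vs 50% (22% with the gate, if 135 and 180 µg are at 50% and 90 µg and placebo at 30%). The pooled 30 vs 210 comparison has 51%, but that extra power comes mostly from subjects who were not randomised concurrently.

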1.4 Sample Size Calculation

The sample size for the Run-in phase has been chosen to allow detection of common AEs with the three initial dose levels. 30 Subjects will provide 95 % confidence that an AE not seen in the Run-in phase would have a true incidence of below 10 %.

The overall group size for the two doses (VLA15 w/ alum 135 µg and VLA15 w/ alum 180 µg) evaluated in the Main Study phase has been selected to provide a sufficient safety database and for determining the optimal dose before advancing the vaccine candidate into Phase 3. Upon completion of the study, the total number of subjects exposed to the dose used for Phase 3 trials would be a minimum of approximately N=210. The database would thus allow 95 % confidence that a given reaction would not be observed at a higher rate than 1:(210/3) rate, i.e. 1.4 %, if it is not observed in the trials preceding Phase 3.

[figure not shown]
With respect to the primary endpoint, GMTs for ST1-6 specific IgGs on Day 85: In the absence of an established protective titer, sample size calculation is based on somewhat arbitrary differences in GMTs between VLA15 treatment groups, in order to demonstrate which titer levels could be distinguished with the proposed sample size. Titers observed in Phase 1 were used as basis: In the 90 µg w/ alum group (i.e. the lowest dose group used in the present Phase 2 study), a GMT of 61.3 was observed for ST1 (i.e. the serotype with lowest titers in Phase 1) with a Standard Deviation (LOG10) of 0.51. A total of 189 subjects per group (assuming 10 % of the 210 subjects per treatment group are excluded from primary Per-protocol (PP) analysis) will provide 80 % power at a two-sided alpha level of 5 % to distinguish a GMT of 61.3 in one treatment group from a putative higher GMT of 86.1 in another dose group. An approximately 1.5 fold higher titer could thus be distinguished. A 1.5 fold difference in GMTs is often considered a relevant difference in vaccine studies, e.g. when setting non-inferiority boundaries.

The overall sample size of 120 subjects in the placebo group has been selected to allow for the internal validation of both safety and immunogenicity results.

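### No between-group risk difference with a confidence interval is planned for adverse events, and dose comparisons depend on a significant four-group test

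*SAP*

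**What the plan says.** SAP Section 6.1.3 is the whole inferential plan for adverse events. It has four parts.

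- Estimation within groups: "95% confidence intervals according to Altman will generally be provided for all AE rates".
- Comparison between groups: "Differences between the four treatment groups will be assessed for significance using Fisher's exact (Fisher-Freeman-Halton) test".
- Condition for comparing any two groups, set in the same sentence: "whereby a significant overall test will be amended by pair-wise tests".
- Scope: "It is stated in detail in Section 7 for which tables such comparisons will be made". In Section 7.1.4 the tables concerned carry only a remark that a statistical test is included. No risk difference, risk ratio or interval for a contrast is listed there.

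The groups compared are 90, 135 and 180 µg and placebo. Section 2.12 adds: "Statistical analyses will pool subjects from both Run-in and Main Study phase". Section 1.4 says that the size of the 135 and 180 µg groups "has been selected to provide a sufficient safety database and for determining the optimal dose before advancing the vaccine candidate into Phase 3".

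**The concern.** Choosing between 135 and 180 µg involves tolerability as well as titers, and Section 1.4 links the group size to both. For titers, Section 5.3 plans least squares mean differences with 95% CIs. For AE rates there is no counterpart: the only planned between-group result is a p-value, and the pair-wise p-values appear only if the four-group test, which includes the 30-subject 90 µg group, is significant.

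At these group sizes, a non-significant overall test is a likely result for infrequent events even when 180 µg carries a real excess. In that case the plan shows separate rates with separate intervals, but no statement about the dose contrast and no limit on the excess that the data still allow. The bounds in Section 1.4 do not fill the gap, because they apply to reactions that are never observed.

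**Working it through.** **Inputs from the SAP.** Run-in: 30 per group. Main Study: 180, 180 and 90 (Section 1.2). Pooled: 90 µg 30; 135 µg 30 + 180 = 210; 180 µg 30 + 180 = 210; placebo 30 + 90 = 120. Section 1.4 confirms 210 and 120.

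**Assumed, because the SAP does not give them.** All AE rates, and alpha 0.05 for the AE tests (Section 1.4 states 5% only for the GMT calculation).

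**The plan's own safety figures reproduce.** Rule of three: 3/210 = 1.43% (exact 1 − 0.05^(1/210) = 1.42%; SAP 1.4%) and 3/30 = 10% (exact 9.5%; SAP 10%). Both concern unobserved events. The SAP claims no power for comparing AE rates.

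**How often the rule gives a dose result.** The four-group Fisher-Freeman-Halton test was enumerated exactly for 30/210/210/120, followed by the two-sided Fisher test of 180 against 135 µg, and outcomes were weighted by their binomial probabilities. The rate is p in three groups and 2p at 180 µg. Missed = 100% − gated.

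| p | Overall test significant | 180 vs 135 µg, gated | 180 vs 135 µg, ungated | Missed, gated |
|---|---|---|---|---|
| 1% | 6.6% | 3.5% | 4.9% | 96.5% |
| 2% | 14.7% | 10.2% | 14.0% | 89.8% |
| 3% | 23.3% | 17.6% | 24.0% | 82.4% |
| 5% | 41.6% | 34.5% | 42.8% | 65.5% |
| 8% | 66.0% | 58.9% | 67.3% | 41.1% |
| 10% | 78.3% | 72.5% | 79.2% | 27.5% |
| 15% | 95.3% | 93.1% | 95.1% | 6.9% |

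At 5% against 10%, the gate costs 42.8 − 34.5 = 8.3 points. The other 100 − 42.8 = 57.2 points of the missed share would remain without it. For 180 µg against placebo at the same rates, the gated figure is 25.9% and the ungated one 31.3%.

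**One possible result.** Take 10/210 at 135 µg, 21/210 at 180 µg, 6/120 on placebo and 1/30 or 2/30 at 90 µg. The overall p is 0.14 or 0.15, so no pair is tested.

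- Wilson intervals by group: 21/210 = 10.0% (6.63 to 14.80); 10/210 = 4.76% (2.61 to 8.54). They overlap.
- Difference: 10.00 − 4.76 = 5.24 points.
- Newcombe lower limit: 5.24 − √[(10.00 − 6.63)² + (8.54 − 4.76)²] = 5.24 − 5.06 = +0.2.
- Newcombe upper limit: 5.24 + √[(14.80 − 10.00)² + (4.76 − 2.61)²] = 5.24 + 5.26 = +10.5.

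The Fisher test for this pair, had it been run, gives p = 0.060; the two methods differ slightly at the border. With 11/210 instead of 10/210, the difference is +4.8 points (−0.4 to +10.1), Fisher p = 0.097. In both cases an excess of about 10 points is not excluded, and the plan would print no such figure.

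**The case against.** The strongest reply is that safety is described, not tested, in this trial. The primary endpoint is the Day 85 GMT, the safety endpoints are frequencies, and Section 6.1.1 calls their analysis descriptive. Every group has its own column and every AE rate its own 95% CI, whatever the overall test shows. No AE comparison was claimed to be powered, and a reader can compute a difference from the counts. This stands in part: the SAP makes no false statement here. But side-by-side intervals do not give the interval for the difference, as the example shows, and the dose contrast should not be left to the reader.

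Four stronger readings are tempting, and the document does not support them.

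- That safety rests on a significance test alone, with no upper bound. Each rate has an interval and therefore an upper limit; what is missing is an interval for the contrast.
- That a doubling at 180 µg is missed in about two thirds of trials. This holds for an assumed 5% against 10% only; the table shows how far it moves with the base rate.
- That the gate causes the misses, or that they breach a 20% limit. Most of the missed share at 5% against 10% comes from 210 per group, and the 80% power in Section 1.4 is for GMTs, not AEs.
- That the sponsor will take a non-significant test as proof of equal tolerability. The SAP contains no such rule.

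Nor is it a fault that placebo would often open the gate for common local reactions: the dose comparison is then made.

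**Conclusion.** The point holds as an omission with a cheap remedy. Section 6.1.3 plans no between-group risk difference with an interval and makes every pair-wise AE comparison conditional on a four-group test. When that test is not significant, the plan says nothing about the size of the 180 versus 135 µg contrast.

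The illustrative figures rest on planned group sizes, assumed AE rates with only 180 µg raised, and an assumed alpha of 0.05. They show that silence is the likely outcome for infrequent events (for a doubling, more than half of trials at a base rate of 5% or less) and unlikely at a base rate of 15%. They are not a property of the plan at all AE rates, and they do not show that removing the gate alone would solve the problem.

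**What to change.** In Section 6.1.3, add risk differences with 95% CIs (Newcombe or Miettinen-Nurminen) for three contrasts: 180 minus 135 µg, 135 µg minus placebo, and 180 µg minus placebo. Report them whether or not the overall test is significant, in the overall Tables 14.1.4.1, 14.1.4.14 to 14.1.4.16 and 14.1.4.20. Leave out Tables 14.1.4.17 to 14.1.4.19, which split by age group, region and serostatus, where some cells will be small.

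Label the intervals descriptive and without multiplicity control. State that the upper limit, not a non-significant p-value, describes the excess that cannot be excluded. Keep the Fisher tests as supportive, and note that interval and test may disagree at the border.

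Cost: a paragraph of SAP text and a few columns in five tables. Output drafts were already reviewed (Section 8), so some reprogramming and renewed review is needed, but no new data or subjects. The downside is more unadjusted intervals to read. They do not raise power.
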